3.2.1 Procedures at Study Visits

366 The following procedures will be performed at each visit, unless otherwise specified:

- Review of study device data
- Assessment of compliance with study device use by review of any available device data
- Assessment of device issues that have occurred
- Assessment of adverse events, using open ended questions to capture hyperglycemic and hypoglycemic events, and their underlying cause and relationship to the study device or other parts of the system (such as the infusion set).

373 At 13 weeks (or if at subject withdrawal), the study staff will then supervise the participants transition
374 back to their standard of care therapy as follows:

375 • Study staff will re-evaluate the subject's baseline therapy doses, noting changes in basal rates,
376 carbohydrate ratios, and correction factors in use at the end of the trial.

377 • The study investigator will supervise and confirm the entry of settings in the insulin delivery profile
378 of the participant's home pump at the end of the study.

379 • Blood draw (venipuncture or fingerstick) for HbA1c measurement at central lab (Device Training
380 Visit and 13 weeks only)

381 **3.2.2 Unscheduled Visits**

382 Participants may have unscheduled visits during the study period if required for additional device training
383 or other unanticipated needs per the study investigator discretion. Study participants will be instructed to
384 upload their study device any time the participant changes device profile settings, and study staff will
385 document review of these changes as an unscheduled visit. Documentation of the review must occur as an
386 unscheduled visit if these changes are not being performed in window/part of the scheduled study visits
387 and are not captured as part of a scheduled study visit.

388 **3.2.3 Exercise and Meal Challenges**

389 Participants will complete 3 meal and 3 exercise challenges during the study. Procedures are described in
390 section 5.1.

391 **3.3 Early Discontinuation of Study Device**

392 Participants who discontinue the study device prior to 13 weeks, either by choice or by investigator
393 decision, will be asked to come for an end of study visit and then will be dropped from the study.
394 If the visit occurs at 6 weeks or after, blood will be drawn for the central laboratory HbA1c measurement.

396

Chapter 4: Study Devices and Drugs

397

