- 602 • Serum ketones > 1.5 mmol/L or large/moderate urine ketones;
- 603 • Either arterial blood pH < 7.30 or venous pH < 7.24 or serum bicarbonate (or CO₂) < 15 ; and
- 604 • Treatment provided in a health care facility

605 When a hyperglycemia/ketotic event qualifies as an SAE as defined in section 6.2.1, an Adverse Event
606 Form should be completed. Events meeting DKA criteria should be considered to be serious adverse
607 events with respect to reporting requirements. Hyperglycemia events not meeting criteria for DKA

608 generally will not be considered as serious adverse events unless one of the SAE criteria in section 6.2.1
609 is met.

610 DKA can occur at “euglycemic” glucose levels less than 250 mg/dL, and may occur more commonly in
611 individuals taking adjuvant medications for glucose control such as SGLT-2 inhibitors. This should be
612 reported as a DKA event if it occurs.

613 When a hyperglycemia/DKA event occurs during use of a study device, it generally will be considered to
614 be unrelated to the device (per section 6.2.5) if the device functioned as intended and there does not
615 appear to be a flaw in how the device is intended to function.

616 **6.2.5 Relationship of Adverse Event to Study Investigational Device**

617 The study investigator will assess the relationship of any adverse event to the study device or study drug.
618 The Medical Monitor also will make this assessment, which may or may not agree with that of the study
619 investigator. Reporting requirements will be based on the Medical Monitor’s assessment.

620 To ensure consistency of adverse event causality assessments, investigators should apply the following
621 general guidelines when determining whether an adverse event is related to a study device or study drug:

622 **Unrelated:** The AE is clearly not related to a study drug/device and a likely alternative etiology exists
623 such as an underlying disease, environmental or toxic factors or other therapy.

624 **Unlikely Related:** The AE does not follow a reasonable temporal sequence during or after use of study
625 drug/device and a more likely alternative etiology exists such as an underlying disease, environmental or
626 toxic factors, or other therapy.

627 **Possibly Related:** The AE occurred in a reasonable time during or after use of study drug/device; but
628 could be related to another factor such as an underlying disease, environmental or toxic factors, or other

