629 therapy; and there is a possible, though weak, scientific basis for establishing a causal association
630 between the AE and the study drug/device.

631 **Probably Related:** The AE occurred in a reasonable time during or after use of study drug/device; is
632 unlikely to be related to another factor such as an underlying disease, environmental or toxic factors, or
633 other therapy; and there is a plausible, though not strong, scientific basis for establishing a causal
634 association between the AE and the study drug/device.

635 **Definitely Related:** The AE occurred in a reasonable time during or after use of study drug/device;
636 cannot be explained by another factor such as an underlying disease, environmental or toxic factors, or
637 therapy; and there is a strong scientific basis for establishing a causal association between the AE and the
638 study drug/device.

639 Events determined to be *Possibly Related*, *Probably Related*, or *Definitely Related* will be considered
640 ‘Related’ with respect to any required IRB and FDA reporting.

641 **6.2.6 Severity (Intensity) of Adverse Events**

642 The severity (intensity) of an adverse event will be rated on a three-point scale: (1) mild, (2) moderate,
643 or (3) severe. A severity assessment is a clinical determination of the intensity of an event. Thus, a severe
644 adverse event is not necessarily serious. For example, itching for several days may be rated as severe, but
645 may not be clinically serious.

646 **MILD:** Usually transient, requires no special treatment, and does not interfere with the participant’s daily
647 activities.

648 MODERATE: Usually causes a low level of inconvenience, discomfort or concern to the participant
649 and may interfere with daily activities, but is usually ameliorated by simple therapeutic measures and
650 participant is able to continue in study.

651 SEVERE: Interrupts a participant's usual daily activities, causes severe discomfort, may cause
652 discontinuation of study device, and generally requires systemic drug therapy or other treatment.

653 **6.2.7 Expectedness**

654 For a serious adverse event that is considered possibly related to study device, the Medical Monitor will
655 classify the event as unexpected if the nature, severity, or frequency of the event is not consistent with the
656 risk information previously described in the protocol, labeling, or Investigator Brochure.

657 **6.2.8 Coding of Adverse Events**

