687 These occurrences are expected and will not be reported on a Device Issue Form assuming criteria for
688 a UADE or ADE have not been met:

- 689 • CGM sensor lasting fewer days than expected per manufacturer
- 690 • CGM tape adherence issues
- 691 • Pump infusion set insertion lasting fewer days than expected per manufacturer
- 692 • Battery lifespan deficiency due to inadequate charging or extensive wireless communication
- 693 • Intermittent device component disconnections/communication failures not requiring system
694 replacement or workaround/resolution not specified in user guide/manual.
- 695 • Device issues clearly addressed in the user guide manual that do not require additional
696 troubleshooting

697 **6.4 Timing of Event Reporting**

698 SAEs possibly related to a study device, study drug, or study participation and UADEs must be reported
699 by the site to the Sponsor within 1 working day of the site becoming aware of the event. This can occur
700 via phone or email, or by completion of the appropriate eCRFs as applicable. If the form(s) are not
701 initially completed, they should be completed as soon as possible after there is sufficient information to
702 evaluate the event. All other reportable ADEs and other reportable AEs should be submitted by
703 completion on the eCRF(s) within 7 days of the site becoming aware of the event.

704 The Sponsor will notify all participating investigators of any adverse event that is serious, related, and
705 unexpected. Notification will be made within 10 working days after the Sponsor becomes aware of the
706 event.

707 Each principal investigator is responsible for reporting serious study-related adverse events and abiding
708 by any other reporting requirements specific to his/her Institutional Review Board or Ethics Committee.

709 Upon receipt of a qualifying event, the Sponsor will investigate the event to determine if a UADE has
710 occurred, and if indicated, report the results of the investigation to all overseeing IRBs, and the FDA
711 within 10 working days of the Sponsor becoming aware of the UADE per 21CFR 812.46(b). The Sponsor
712 must determine if the UADE presents an unreasonable risk to participants. If so, the Sponsor must ensure
713 that all investigations, or parts of investigations presenting that risk, are terminated as soon as possible but
714 no later than 5 working days after the Sponsor makes this determination and no later than 15 working

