743 participant behavior contrary to the indications for use of the device that imposes on the participant's
744 safety
- 745 • The participant requests that the treatment be stopped
- 746 • Participant pregnancy
- 747 • Two distinct episodes of DKA as defined in section 6.2.4
- 748 • Two distinct severe hypoglycemia events as defined in section 6.2.3
- 749 • One episode of DKA as defined in section 6.2.4 and one severe hypoglycemia event as defined in
750 section 6.2.3

751 Each DKA or severe hypoglycemia event will be reviewed by the Medical Monitor with respect to
752 determination of cause and whether the occurrence of the event can be attributed to use of the study
753 device or study drug.

754 An additional requirement for continued study device use following a single DKA or severe
755 hypoglycemia event will be that the site investigator believes that the event is unlikely to recur and that
756 it is safe for the participant to continue to use the system. Additionally, if the Medical Monitor determines
757 that the occurrence of the event indicates that it is not safe for the participant to continue to use the study
758 device, use will be discontinued.

759 **6.6.2 Criteria for Suspending or Stopping Overall Study**

760 In addition to the suspension of device use due to a UADE as described in section 6.6.1, study activities
761 could be similarly suspended if the manufacturer of any constituent study device requires stoppage of
762 device use for safety reasons (e.g. product recall). The affected study activities may resume if the
763 underlying problem can be corrected by a protocol or system modification that will not invalidate the
764 results obtained prior to suspension.

765 Closed-loop system use will also be suspended if there are three or more cases of severe hypoglycemia or
766 three or more cases of hyperglycemia/ketotic events qualifying as SAEs across the entire study in
767 participants who have initiated Control-IQ technology use. The IRBs and FDA will be notified. After
768 assessment of the problem and any corrections are implemented, use of the closed-loop system may be
769 restarted if approval is received from the IRBs and FDA.

770

771

Confidential

Contains trade secrets and/or confidential information exempt from disclosure from 21 CFR 20.61

Chapter 7: Miscellaneous Considerations

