7.1 Drugs Used as Part of the Protocol

774 Subjects may use their own Humalog (insulin lispro) or Novolog (insulin aspart) during the Treatment
775 Period, however, Humalog or Novolog will be provided to the subject as part of the study.

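### Section 6.6.2 counts severe hypoglycemia and ketotic SAEs toward study-wide suspension whatever their cause, but section 6.4 allows up to 7 days to report those not judged possibly related

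*Combined protocol and SAP*

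**What the plan says.** Section 6.6.2 gives two study-wide triggers. The first reads "Closed-loop system use will also be suspended if there are three or more cases of severe hypoglycemia or"; the second is "three or more cases of hyperglycemia/ketotic events qualifying as SAEs across the entire study in" participants who have started Control-IQ. Having started Control-IQ is the only qualifier. Relatedness is not mentioned.

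Section 6.4 sets the site-to-Sponsor deadlines. "SAEs possibly related to a study device, study drug, or study participation and UADEs must be reported" within 1 working day of site awareness. Every other reportable event is entered on the eCRF "within 7 days of the site becoming aware of the event".

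Four other parts of the protocol bear on this:

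- **6.2.3 and 6.2.4** class severe hypoglycemia and DKA as SAEs for reporting. They add that such events will generally be considered unrelated to the device if it worked as intended.
- **6.2.5** defines the causality categories. Possibly Related needs only a "possible, though weak, scientific basis for establishing a causal association". It also says "Reporting requirements will be based on the Medical" Monitor's assessment.
- **6.5** has the Medical Monitor typically review SAEs within 1 working day, counted from reporting.
- **6.6.1** has the Medical Monitor review each DKA or severe hypoglycemia event and sets conditions for the affected participant to continue.

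**The concern.** The suspension rule and the reporting clock use different criteria. Section 6.6.2 counts events by type and seriousness; section 6.4 speeds them up by relatedness. With up to 5 sites (section 2.1), no single site sees the study-wide total, so the count can be kept only from reports that reach the Sponsor. If one of the counted events is on the 7-day route, the threshold may have been met for some days before anyone is in a position to know it, and the other participants remain on closed loop meanwhile. No formal interim analysis is planned (section 8.10), so these counts are the only numeric study-wide trigger in the document.

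**Working it through.** The plan gives no figure to reproduce here. The check has three parts.

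**1. Which counted events can take the slow route?** An event must be judged not possibly related on all three limbs of section 6.4: device, drug and participation.

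- *Device.* The default in 6.2.3 and 6.2.4 removes this limb when the device worked as intended. By itself it does not put an event on the slow route.
- *Drug.* Section 7.1 lists insulin among drugs used as part of the protocol ("however, Humalog or Novolog will be provided to the subject as part of the study"), although the term study drug is not formally defined. With the low bar in 6.2.5, most severe hypoglycemia should qualify as possibly related.
- *Participation.* This limb is broad, but the categories in 6.2.5 are worded for study drug and device only, so sites have no scale for it.

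Ketotic SAEs leave more room. Section 3.2.1 asks about an event's "relationship to the study device or other parts of the system (such as the infusion set"), which treats the infusion set as separate from the study device, and 6.4 does not name it. SGLT-2 inhibitors are allowed under 7.3, are not listed in 7.1, and are named in 6.2.4 in connection with euglycemic DKA. A site could attribute an event to either cause, though it could also rate it possibly related.

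**2. How long can recognition be delayed?** Recognition is the day the third counted report arrives.

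- Largest extra lag per event: 7 − 1 = 6 days. If the working day runs from Friday to Monday (3 calendar days): 7 − 3 = 4 days.
- No single report is more than 6 days later than on the fast route, so the third report cannot be more than 6 days later either.

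Example with counted events known to sites on days 0, 2 and 7:

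| Event on 7-day route | Reports arrive on days | Third report | Delay |
|---|---|---|---|
| None | 1, 3, 8 | 8 | – |
| Day-2 event | 1, 9, 8 | 9 | 1 day |
| Day-7 event | 1, 3, 14 | 14 | 6 days |

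If the slow reports have all arrived before a fast third one, the delay is 0. The range is therefore 0 to 6 days.

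The number of concurrent users is not given. Assuming 30, with a range of 10 to 60, a 6-day delay is 6 × 30 = 180 participant-days of closed-loop use (60 to 360). A 4-day delay is 4 × 30 = 120 (40 to 240).

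**3. How likely is the trigger to be reached?** Exposure for 30 completers over 91 days is 30 × 91 / 365.25 = 7.47 person-years. Three events of one type correspond to 3 / 7.47 = 40 per 100 person-years. The true rates below are assumptions, since the documents give none. The probability is P(X ≥ 3) for a Poisson count with mean equal to rate × 7.47.

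| Assumed rate per 100 person-years | Mean | P(three or more) |
|---|---|---|
| 5 | 0.37 | 0.7% |
| 10 | 0.75 | 4.0% |
| 20 | 1.49 | 19% |

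These are chances per event type of reaching the trigger, not of reaching it late.

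**The case against.** The strongest reply is that the gap is narrow.

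- **The participation limb is wide.** Section 1.3.1.4 lists ketonemia from a pump or infusion set that is not working properly as a known study risk. A site would find it hard to call such an event not even possibly related to participation.
- **SGLT-2 users have added safeguards.** Sections 3.1.1 and 3.1.3 provide for scheduled ketone checks, withdrawal after repeated raised values, and instructions for illness. These should make ketotic events rarer.
- **The Medical Monitor may learn of events early.** Section 6.2.5 gives the governing assessment to the Monitor, who is the Sponsor's Medical Director. The single-event review in 6.6.1 gives the site a reason to call promptly.
- **The chance of a late trigger is small.** Suppose 10% to 50% of counted events were slow and delay arose mainly when the third was slow. Multiplying the probabilities above by 0.1 and 0.5 gives roughly 0.07–0.3%, 0.4–2% and 2–10%.
- **Another document may close the gap.** Section 6.5 refers to a safety management plan, which may set a shorter deadline.

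Most of this stands as a limit on frequency, but none of it sets a deadline. The Monitor cannot reclassify or review an event that has not been reported, so in practice the site's first judgment fixes the clock, although 6.4 does not say whose judgment applies. The continuation conditions in 6.6.1 concern the affected participant only. Section 9.3 prioritizes adverse events for monitoring without giving a time limit.

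**Conclusion.** The mismatch is real and should be corrected. Events that count toward study-wide suspension may lawfully arrive up to 7 days after site awareness. Recognition of the third can be delayed by 0 to 6 days, or at most 4 if the working day spans a weekend. Seven days is a ceiling, and sites may report sooner.

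The gap should be uncommon for severe hypoglycemia and is more plausible for ketotic SAEs. It matters only if the trigger is reached, which is improbable at the lower assumed rates. A suspension rule exists, however, for the case where the device does worse than expected, and that is when late recognition costs most. Endpoint rates are not affected.

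Confidence is medium, because the safety management and monitoring plans were not available and may already require faster reporting. If they do, section 6.4 should agree with them.

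**What to change.** Add one sentence to section 6.4: every event counted in section 6.6.2 (severe hypoglycemia, and DKA or any other hyperglycemia/ketotic event qualifying as an SAE) is to be reported by the site to the Sponsor within 1 working day of awareness, regardless of relatedness. Bring the safety management plan into line if it differs.

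The cost is a few extra expedited site reports. No threshold, dose or clinical rule changes.

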7.1 Drugs Used as Part of the Protocol

774 Subjects may use their own Humalog (insulin lispro) or Novolog (insulin aspart) during the Treatment
775 Period, however, Humalog or Novolog will be provided to the subject as part of the study.

7.2 Collection of Medical Conditions and Medications

777 *Pre-Existing Conditions*: Any medical condition that is either present at screening, a chronic disease,
778 or a prior condition that could impact the participant's health during the course of the study (e.g., prior
779 myocardial infarction or stroke) will be recorded.

780 *Medical Conditions Developing During the Study:* Medical conditions developing during the study will
781 be reviewed by the investigator for their relationship to the study device.

782 Medications: All medications in use at the time of screening or added during the course of the study will
783 be recorded. Nutraceuticals and preventative treatment also will be recorded. Medications only taken as
784 needed either can be recorded when prescribed or only recorded if used during the study. Glucagon for
785 treatment of severe hypoglycemia will only be recorded if used during the study.

7.3 Prohibited Medications, Devices, Treatments, and Procedures

787 Treatment with any insulin other than Humalog or Novolog insulin is not permitted with the study device.

788 Treatment with sulfonylureas, meglitinides or Symlin is not permitted.

789 No new additional non-insulin glucose lowering medications may be added during the trial.

790 Participants taking GLP-1 receptor agonists, DPP-4 inhibitors, and/or SGLT-2 inhibitors will be allowed
791 to continue these medications if they are on a stable dose of such medication for the last 3 months. These
792 participants will be instructed to perform additional glucose and ketone monitoring as specified in section
793 3.1.3 Training on Management of Hyperglycemia and 3.1.2 Training on Management of Hypoglycemia.

794 Medications used for weight loss will be allowed if the participant is on a stable dose of such medication
795 for the last 3 months. No new medications for weight loss may be added during the trial.

796 Additional medications may be excluded per judgement of the investigator.

797 The investigational study devices (t:slim X2 insulin pump, Dexcom CGM sensor) must be removed
798 before magnetic resonance imaging (MRI), computed tomography (CT) or diathermy treatment.
799 Participants may continue in the trial after temporarily discontinuing use if requiring one of the above.

800 7.4 Rescue Medications, Treatments, and Procedures

801 Each participant will be required to have a glucagon preparation for rescue therapy for severe
802 hypoglycemia.

803 7.5 Pregnancy Reporting

804 If pregnancy occurs, the participant will be discontinued from the study. The occurrence of pregnancy
805 will be reported to the Coordinating Center within seven days and to the IRB as an Unanticipated
806 Problem within seven calendar days.

807 **7.6 Participant Compensation**

808 Participant compensation will be specified in the informed consent form.

809 **7.7 Participant Withdrawal**

810 Participation in the study is voluntary, and a participant may withdraw at any time. For participants who
811 withdraw, their data will be used up until the time of withdrawal.

812

Chapter 8: Statistical Considerations

